APPENDIX II

List of procedures / visits and schedule of events

A. List of procedures per visit

Baseline Visit	
• Read and sign this informed consent form (ICF).• If you are a pre-menopausal woman, confirm that you are not pregnant by a urine pregnancy test.• Have a medical history assessment, a physical, and record vital signs.• Have your blood drawn and collect urine.• Arterial Tonometry / VaSera test.• Have a Doppler Echocardiogram.• Complete the MRI of your Heart.• Setup the 24 Hour BP monitoring and pulse wave analysis watch.• Medication given out.• Bicycle Exercise Test• Activity Monitor
Week 1 Visit	
• Collect Vital Signs.• Review Side Effects• Increase medication dose to 60 mg daily.• Collect medication of the previous dose.• Arterial Tonometry / VaSera test.• Download and replacement of pulse wave analysis watch• Blood draw and urine collection• 24 Hour BP Monitoring• Activity Monitor
Week 2 Visit	
• Collect Vital Signs.• Review Side Effects• Increase medication dose to 120 mg daily.• Collect medication of the previous dose.• Download and replacement of pulse wave analysis watch• Collect information on potential side effects.• Arterial Tonometry / VaSera test.• Replace pulse wave analysis watch.

	
 • Medication given out. • Arterial Tonometry and VaSera • 24 Hour BP Monitoring • Activity Monitor
Week 3 Visit	
 • Collect Vital Signs. • Review Side Effects • 24 Hour BP Monitoring and pulse wave analysis watch Arterial Tonometry / VaSera test. • Have a Doppler Echocardiogram. • Bicycle Exercise Test • Blood Draw and urine collection • Activity Monitor: 2 weeks prior visit
3 Month Visit	
 • The Arterial Tonometry and VaSera test. • Have a Doppler Echocardiogram. • Setup the 24 Hour BP monitoring and pulse wave analysis watch. • Medication given out. • Activity Monitor: 2 weeks prior to the visit • Review Side Effects • Blood Draw and urine collection
6 Month Visit	
 • If you are a pre-menopausal woman, confirm that you are not pregnant by a urine pregnancy test • Have a medical history assessment, a physical, and record vital signs. • Review Side Effects • Have your blood drawn and urine collection. • The Arterial Tonometry and VaSera test. • Have a Doppler Echocardiogram. • Complete the MRI of your Heart. • Setup the 24 Hour BP monitoring and pulse wave analysis watch. • After 2 days of wearing pulse wave analysis watch, discontinue the medication. • Bicycle Exercise Test • Activity Monitor: 2 weeks prior to the visit

B. Schedule of events

Test	Baseline visit	Week 1	Week 2	Week 3	Week 12	Week 24
Medical History	X					X
Physical	X					X
Vital Signs	X	X	X	X	X	X
Potential change in study medication		X	X	X		
Arterial Tonometry and VaSera	X	X	X	X	X	X
Doppler Echocardiogram	X			X	X	X
• 24 Hour BP Monitoring	X			X	X	X
• Pulse wave analysis watch	X	X	X	X	X	X
• Cardiac MRI	X					X
• Blood draw and urine collection	X	X	X	X	X	X
Review Side Effects		X	X	X	X	X
Activity Monitor	X	X	X	X	2 weeks prior to the visit	2 weeks prior to the visit
Bicycle Exercise Test	X			X		X

References

1. Dhingra R, Gaziano JM and Djousse L. Chronic kidney disease and the risk of heart failure in men. *Circ Heart Fail.* 2011;4:138-44.
3. [name] JA, Khan A, Bansal N, Dries DL, Feldman HI, Ford V, Anderson AH, Kalle R, Lash JP, Ojo A, Schreiber M, Sheridan A, Strelsin J, Teal V, Roy J, Pan Q, Go AS, [name] RR, Investigators CS and Investigators CS. Arterial stiffness, central pressures, and incident hospitalized heart failure in the chronic renal insufficiency cohort study. *Circ Heart Fail.* 2014;7:709-16.
4. Centers for Disease Control and Prevention. National Chronic Kidney Disease Fact Sheet: General Information and National Estimates on Chronic Kidney Disease in the

Targeting Central Hemodynamics in CKD Pilot Study
Protocol Version 003, February 15, 2016

United States, 2010. Atlanta, GA: U.S. Department of Health and Human Services, CDC; 2010.

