- 1) **To establish the feasibility** of reducing wave reflections while minimizing changes in brachial blood pressure. By performing assessments of the effects of 3 different doses of SR ISMN on office and 24-hour blood pressure and wave reflections, we aim to determine which dose of this drug best reduces wave reflections with the least impact on brachial blood pressure in this particular population. This will directly support secondary aim 1 of the RO1 application and will inform about the best dose to use in the definitive RO1-funded trial/application. We will also assess whether vitamin C reduces the tolerance to nitrate therapy over time.
- 2) We will gather preliminary data regarding the feasibility of using an **unbiased biomarker discovery approach** to identify biomarkers/pathways that change with ISMN administration in our 20 subjects. We will utilize a novel proteomic approach (Somasscan) to measure levels of 1,129 candidate biomarkers at baseline and after ISMN. We eventually want to identify novel biomarkers/pathways that correlate with the cardiac response to ISMN.
- 3) To assess the variability in changes in **aerobic capacity** (peak oxygen consumption during maximal supine bicycle exercise test), **vasodilatory reserve to exercise** (reduction in systemic vascular resistance with exercise, measured with Doppler echocardiography), and **physical activity** (assessed via actigraphy) with ISMN administration.

B. BACKGROUND AND SIGNIFICANCE

Heart failure (HF) is a major epidemic.

Heart Failure (HF) affects ~2.4% of the US population and 10% of individuals aged >75 years. The burden of HF has increased dramatically over the last few years, vastly exceeding previous projections (Figure 1). According to the American Heart Association^{13, 14} the number of new HF cases in the US increased from 348,000 in 2000 to 670,000 in 2007, representing a 93% increase over this time period. Not only is HF already an epidemic, but with the aging of the population, a dramatic further increase in its prevalence is expected.

Figure 1. The Epidemic of Heart Failure. Projected burden of HF in the US according to previous projectors (solid line) vs. actual burden (dotted line) From: Lam et al. European journal of heart failure. 2011;13:18-28

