
Figure 6. Hazard curves for incident of Heart Failure among 5,958 MESA participants stratified according to the presence or absence of hypertension (prevalence=45%) or the presence or absence of "high" reflection magnitude (top 45% of the population). Hazard curves are adjusted for other significant predictors of HF in this population. From: [name] JA et al, *J Am Coll Cardiol*: 60:2170-2177.

Targeting Central Hemodynamics in CKD Pilot Study
Protocol Version 003, February 15, 2016

highly desirable goal from the clinical and public health perspective. In order to design a definitive proof of concept trial, we must first establish the optimal dose of ISMN to reduce wave reflections independently of blood pressure and to assess the variability in study endpoints in response to ISMN in this particular population, such that adequate power calculations can be made.

C. RESEARCH DESIGN AND METHODS

C.1. Overview of study design

This is a pilot study in which we will study 20 subjects with CKD. We will perform a run-in phase in which the dose of sustained-release ISMN (SR-ISMN) will be increased from 30 to 120 mg over weeks. We will administer 30 mg for 1 week, followed by 60 mg for 1 week, followed by 120 for 1 week. At the end of each week, we will perform detailed assessments of blood pressure and central hemodynamics. We will assign half of the participants to receive vitamin C (500 mg three times daily) to assess whether this intervention reduces nitrate tolerance.

After the initial 3-week run in phase, we will randomly assign subjects to receive either 60 or 120 mg of SR-ISMN for additional 21 weeks (for a total of 24 weeks of therapy). Half of the subjects will continue to receive vitamin C (500 mg three times daily by mouth) throughout this 21-week period. We will assess the effect of our interventions on late systolic load, LV mass, LV fibrosis, diastolic relaxation and quality of life.

After subjects are identified and demonstrate an interest in the research study, inclusion and exclusion criteria will be assessed and if eligible, the patients will undergo written informed consent and enrolled in the study.

C.2 Study Sites

The two sites for this trial will be the Hospital of the University of Pennsylvania and the Penn Presbyterian Medical Center. Both sites share a single Institutional Review Board.

C.3. Study Population

[figure not shown]

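### The run-in 24-hour blood pressure recordings are scheduled inconsistently: those for 30 and 60 mg may be missing, or may be made partly on the next dose

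*Combined protocol and SAP*

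**What the plan says.** Secondary aim 1 rests on "assessments of the effects of 3 different doses of SR ISMN on office and 24-hour blood pressure and wave reflections", and is meant to identify the dose that lowers wave reflections most with least effect on brachial pressure. Section C.1 sets the timing: "At the end of each week, we will perform detailed assessments of blood pressure and central hemodynamics". Section D analyses the run-in with mixed models of within-subject change across 30, 60 and 120 mg.

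Three places schedule the recordings:

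- **Appendix II A.** Week 1 has "Increase medication dose to 60 mg daily" and Week 2 has "Increase medication dose to 120 mg daily". Both visits also list collection of the previous dose's tablets and 24-hour monitoring. Week 3 lists "24 Hour BP Monitoring and pulse wave analysis watch Arterial Tonometry / VaSera test" and shows no dose change.
- **Section C.5.** 24-hour monitoring is named only at the 3-week visit. The 1-week and 2-week visits have tonometry and VaSera, then the dose increase.
- **Appendix II B.** 24-hour monitoring is marked at baseline and Weeks 3, 12 and 24, not at Weeks 1 or 2. The row "Potential change in study medication" is marked at Weeks 1, 2 and 3.

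Section C.5 also assigns 10 subjects to 60 mg and 10 to 120 mg once the run-in is complete.

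Elsewhere the plan does order drug and measurement. C.5 starts ISMN after the baseline assessments, and the 6-month entry reads "After 2 days of wearing pulse wave analysis watch, discontinue the medication".

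**The concern.** Clinic tonometry at a dose-change visit looks back at the dose in force. A 24-hour recording looks forward if the monitor is put on at that visit. With the earlier tablets handed in, an up-titrated subject's next tablet is the new strength, so the later hours of a recording labelled with the old dose would belong to the new one. No text for Weeks 1 and 2 says which comes first.

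The alternative schedule avoids the overlap by having no recording at those visits, which leaves two of the three doses without run-in 24-hour data. Either way, the 24-hour part of the comparison meant to inform the dose for the definitive trial is weakened. Tonometry and VaSera, done within the visit, do not have this problem.

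**Working it through.** The plan gives no figure tied to this point, so there is nothing to reproduce. The check sets the sources side by side and then asks how much of a recording could fall on the next dose.

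**Step 1: the sources**

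| Visit | Dose up to visit | Medication change | 24-h BP in C.5 | in App. II A | in App. II B |
|---|---|---|---|---|---|
| Week 1 | 30 mg | raised to 60 mg | no | yes | no |
| Week 2 | 60 mg | raised to 120 mg | no | yes | no |
| Week 3 | 120 mg | potential change in B; none listed in A | yes | yes | yes |

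Under C.5 and Appendix II B, the run-in yields recordings at baseline and at the end of 120 mg only.

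**Step 2: share of a recording on the next dose (Appendix II A followed)**

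Let the monitor be fitted at clock hour v and the first new tablet be taken next morning at hour m. The recording ends at v + 24 and the tablet is taken at m + 24, so the share is f = (v − m)/24. The protocol gives neither v nor m; the appended label says morning dosing. All clock times below are assumptions.

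- Monitor worn before the visit and returned at it: f = 0%.
- Tablet 07:00, fitted 10:00: 3/24 = 12.5%. Fitted 14:00: 7/24 = 29%.
- Wider range: tablet 08:00, fitted 08:00: 0/24 = 0%. Tablet 06:00, fitted 16:00: 10/24 = 42%.
- New dose taken at the visit: up to 24/24 = 100%.

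**Step 3: mean dose behind each label (illustration)**

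Assume a clean baseline, every subject up-titrated, and the 10 of 20 assigned to 60 mg stepping down at once at Week 3. The time-weighted mean doses are 30 + 30f, 60 + 60f and 120 − (10/20)(60f) = 120 − 30f.

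- f = 12.5%: 33.75, 67.5 and 116.25 mg.
- f = 29% (7/24): 38.75, 77.5 and 111.25 mg.
- f = 100%: 60, 120 and 90 mg. The recordings labelled 60 and 120 mg change order.

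**Step 4: effect on a linear dose slope (illustration)**

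Regress on the labels 0, 30, 60 and 120 (mean 52.5). The sum of squares is 52.5² + 22.5² + 7.5² + 67.5² = 7,875. If the effect is linear in time-weighted dose, the slope changes by [(−22.5)(30f) + (7.5)(60f) + (67.5)(−30f)]/7,875 = −2,250f/7,875 = −0.286f. The fitted slope is therefore 0.96 of the true slope at f = 12.5%, 0.92 at 29% and 0.71 at 100%. If Week 3 is clean, the change is −225f/7,875 = −0.029f, and the slope stays at 0.97 even at f = 100%.

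**The case against.** A reader might infer that the monitor is fitted at the dose-change visits, that the 24-hour recordings therefore run into the next dose, and that all 20 subjects are affected. The documents do not support that.

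- The baseline, 3-month and 6-month entries speak of setting the monitor up; the Week 1 to 3 entries do not. C.1 places assessments at the end of each week, so a recording worn before the visit is compatible with the text.
- Appendix II A is a list, not a sequence. At Week 1 it puts the dose increase before tonometry.
- Weeks 1 and 2 rest on Appendix II A alone. If C.5 and Appendix II B govern, the data are absent, not mislabelled.
- At Week 3, Appendix II A shows no dose change, and C.5 assigns the long-term dose only after the run-in is complete, which may itself be the ordering. Subjects assigned to 120 mg do not change dose.
- Up-titration is conditional on blood pressure, orthostasis and symptoms, so not every subject need change dose.
- With next-morning dosing the slope distortion is small, in a pilot that already declares limited power.

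All of this stands, and it limits the claim to what may happen. It does not clear the plan. No text describes fitting the blood pressure monitor before the visit. Where pre-visit wear is intended, as for the activity monitor before Weeks 12 and 24, the protocol says so. Nor does the other schedule supply the data. The Week 12 and 24 recordings cover 60 mg only in the 10 subjects assigned to it, after long-term therapy, and never cover 30 mg. The pulse wave watch is scheduled at Weeks 1 and 2, but it is described as recording the radial pulse and transit time, not brachial pressure.

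**Conclusion.** The point holds as a conflict between sections together with an unstated order, not as a demonstrated mislabelling.

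Under C.5 and Appendix II B, the run-in has no 24-hour recording at 30 or 60 mg. This needs no assumption. Under Appendix II A, the recordings for those doses may be made partly or wholly on the next dose: 0% if worn beforehand, about 12.5% to 29% with next-morning dosing under the assumed clock times (0% to 42% over the wider range), and up to 100% if the new dose starts at the visit. At Week 3, the one run-in recording on which all three sources agree, up to 10 of 20 subjects may be affected unless the assigned dose takes effect only after the recording.

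The slope and mean-dose figures are illustrations that assume a linear, time-weighted effect. Staff cannot tell from the text which case applies, so practice may differ between subjects. The point should be settled because the 24-hour data feed the dose comparison for the definitive trial. The primary aims and the clinic tonometry are untouched.

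**What to change.** Reconcile C.5, Appendix II A and Appendix II B on two matters: which run-in visits include 24-hour monitoring, and the order of each recording relative to the dose change, Week 3 included. The result should give each dose named in secondary aim 1 a recording attributable to it. The sponsor decides the timing.

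In data capture, record monitor start and stop times and the time and strength of each tablet around the recording. In section D, state that the dose actually taken during each recording enters the run-in mixed model. Flag readings made after a dose change, and run a sensitivity analysis that excludes them.

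The cost is a few sentences and slightly more data capture. Where a dose change intervenes, the usable recording is shorter and loses hours that follow the morning tablet, so the restricted mean no longer covers a full 24 hours. For that reason the exclusion belongs in a sensitivity analysis.
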